10.5 Adjusted analysis

All analyses will be adjusted for the minimisation variables, baseline age (<80 v \geq 80years), stroke severity (NIHSS score <12 v \geq 12) and trial centre. Given the large number of centres involved, mixed effects regression models will be used, with trial centre included as a random effect.

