7.3 Randomisation

Patients will be randomised 1:1 to the following drug regimens:

- Intervention arm: Clarithromycin 500mg twice daily for 5 days total (route of administration will be determined by the local clinical team based on clinical condition and availability of route of administration in line with local IVOS policy) in addition to usual non-macrolide antibiotic treatment.
- Usual care: Local stroke unit usual non-macrolide antibiotic treatment.

A mixed minimisation/randomisation method designed to maintain balance with respect to baseline age (<80 v \geq 80 years), stroke severity (National Institutes of Health Stroke Scale (NIHSS) score <12 v \geq 12) and trial centre will be applied.

The randomisation list, the program that generated it and the random seed used will be stored in a secure network located within the Robertson Centre for Biostatistics (RCB), accessible only to those responsible for provision of the randomisation system.

CLASP

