7.5 Baseline data

Baseline information will be collected from consented participants that meet all eligibility criteria. This includes but is not limited to:

- Baseline demographics:
 - Date of birth
 - Sex
 - Ethnicity
 - Pre-stroke mRS
 - Baseline EQ-5D-5L
- Time since symptom onset or last seen well to admission and randomisation
- Vascular risk factors:
 - Hypertension
 - Smoking history
 - Alcohol intake
 - Atrial fibrillation
 - Diabetes
 - Dyslipidaemia
 - Coronary artery disease
 - Peripheral vascular disease
 - Previous stroke
- Selected past medical history:
 - Chronic lung diseases
 - Cancer
 - Dementia
 - Medications at baseline
- Stroke subtype:
 - Acute ischaemic stroke
 - Intracerebral haemorrhage
- Baseline stroke severity at admission (NIHSS score)
- Thrombolysis and/or thrombectomy treatment
- Current nutritional status:
 - Nil by mouth
 - Normal diet and fluids
 - Modified diet and fluids
 - Nasogastric tube feeding
 - Peripheral parenteral nutrition
- Previous treated infection earlier in this admission and/or 6 weeks prior to enrolment

CLASP

- Highest recorded in the 72 hours preceding randomisation:
 - Plasma CRP concentration (mg/L)
 - White blood cell (WBC) count and neutrophil count
 - RR (/minute)
 - Temperature (°C)
 - NEWS-2 score
- Lowest oxygen saturations (%)
- Oxygen requirements
- Presence of unilateral or bilateral chest signs on examination
- Clinical chest X-ray (CXR) or other radiology findings
- Antibiotic treatment since admission including initial antibiotic treatment plan
- Health and social care resource use
- Caregiver quality of life (EQ-5D-5L)

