10 STATISTICS AND DATA ANALYSIS

10.1 Sample size calculation

In our preliminary study of antibiotic classes [36] based on observational data we reported a common Odds Ratio (OR) of approximately 0.5 for those receiving macrolides. This observation was not a pre-specified hypothesis. We have applied the 'rule of thumb' to target an effect size that is half that observed in such circumstances. Working on the log OR scale, half the effect size can be back-transformed to our target OR of 0.7.

A sample size of 524 participants per group would give 90% power at a two-sided 5% significance level to detect a common OR of 0.7. This is based on analysis by ordinal logistic regression of the mRS at 90 days, assuming the distribution of 90 day mRS in the control arm to be 2:8:8:5:20:20:37 across mRS 0-6. We propose an adaptive (group sequential) design, with an interim analysis after 50% have provided primary outcome data. If the interim analysis z-statistic for the treatment effect is less than -3.09 (i.e. is in favour of clarithromycin at a one-sided p<0.001), then we shall stop the trial for efficacy. If the interim analysis statistic is greater than -0.5, we shall stop for futility. Otherwise, we shall complete the trial as planned, without adjustment of the final analysis p-value.

Simulations of this approach under alternative assumptions regarding the true common OR (N=10,000 simulated trials at ORs from 0.5 to 1.0) suggest that there is minimal loss of power, and no inflation of the Type I error rate (see Table 3 below). Under the null hypothesis of no treatment effect, the one-sided probability of a false positive result is 0.025, slightly lower than running the full trial (0.026), and there is a 69% probability that the trial will stop early for futility, leading to an expected total sample size of 685. If the true OR is equal to 0.7 (the target value

Version 1.0 – 12 December 2024

CLASP

for the sample size calculation), the power of the adaptive design is 88.3%, close to that achieved by running the full trial (89.8%), but with 25.5% chance of trial stopping early (21.7% for efficacy, 3.8% for futility), the expected sample size is 914. Should the true common OR be 0.5 (as observed in observational studies), the adaptive approach gave a positive result in all simulated trials, with 91.7% stopping early, leading to an expected sample size of 568 (Table 3).

| | Standard Approach | | Adaptive Approach | | | |

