10.4 Subgroup analyses

Subgroup analyses are planned in relation to:

- Age (<80 v ≥80 years)
- Sex (male v female)
- Baseline NIHSS (<12 v ≥12)
- Pre-morbid mRS (0-1 v 2-3 v 4-5)
- Ethnicity (white v non-white)
- Stroke type (ischaemic stroke v ICH)
- Interval since admission (<72 v 73-168 v 169-336 hours)
- Received thrombolysis (yes v no)
- Received thrombectomy (yes v no)
- Highest recorded CRP concentration prior to starting antibiotics (<75 v ≥75 mg/l)
- Highest recorded NEWS-2 score prior to starting antibiotics (dichotomised at median)

Differences in treatment effects between subgroups will be assessed by extending the primary analysis regression model to include treatment-by-subgroup interactions. Within-subgroup treatment effects estimates will be reported with 95% CIs, interaction p-values will be reported, and results will be presented with a forest plot.

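### Section 10.5 enters age and NIHSS in the primary model only as two-way splits and does not name pre-stroke mRS, so efficiency from data already collected is forgone

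*Protocol*

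**What the plan says.** Section 10.5 of the protocol sets the adjustment: "All analyses will be adjusted for the minimisation variables". It writes out the coding as age (<80 v ≥80 years), NIHSS (<12 v ≥12) and trial centre, with centre fitted as a random effect because there are many centres. These are the factors, in the form, that section 7.3 uses for minimisation.

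Section 7.5 collects more detail than that. It lists date of birth, "Pre-stroke mRS" and "Baseline stroke severity at admission (NIHSS score". Pre-stroke mRS reappears in section 10.4 as a subgroup factor, "Pre-morbid mRS (0-1 v 2-3 v 4-5", but is not named as a covariate for the primary outcome. In section 10.3.3, EQ-5D-5L at 90 days is adjusted for its own baseline value.

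The sample size in section 10.1 is stated without reference to covariates: "A sample size of 524 participants per group would give 90% power at a two-sided 5% significance level to detect a common OR of 0.7".

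**The concern.** Splitting age and NIHSS in two discards the prognostic information within each half: an NIHSS of 12 and one of 25 are treated alike. Pre-stroke mRS is the outcome scale measured before the stroke. The eligibility criteria in section 6 set no limit on it, and section 10.4 plans for values up to 5, so some spread is expected. A participant already at pre-stroke mRS 4 is unlikely to reach a good 90-day score on either arm. The model nevertheless treats that person like someone at pre-stroke mRS 0 in the same age and NIHSS cell.

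In a proportional-odds model, conditioning on prognostic baseline variables raises the power of the treatment test and removes chance imbalance within the coarse strata. At stake is information that the trial will hold anyway. Because section 10.5 writes the cuts into the protocol for all analyses, a statistical analysis plan using the continuous values would depart from it.

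**Working it through.** **1. Reproduce the plan's own figure.** Inputs from section 10.1: two-sided 5%, 90% power, a common odds ratio ("half the effect size can be back-transformed to our target OR of 0.7"), and the control distribution ("assuming the distribution of 90 day mRS in the control arm to be 2:8:8:5:20:20:37 across mRS 0-6"). Allocation is 1:1 (7.3). Whitehead's formula for a proportional-odds comparison is

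n per arm = 6(z₀.₉₇₅ + z₀.₉₀)² / [ln(OR)² × (1 − Σ p̄ₖ³)],

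where p̄ₖ is the mean of the two arms' proportions in category k.

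- An OR of 0.7 in the direction of benefit gives treated-arm proportions 0.028, 0.109, 0.102, 0.060, 0.220, 0.190, 0.291.
- Averaged with the control arm: 0.024, 0.0945, 0.091, 0.055, 0.210, 0.195, 0.3305. The cubes sum to about 0.0546.
- n = 6 × (1.960 + 1.282)² / [0.3567² × 0.9454] ≈ 63.04 / 0.1203 ≈ 524.2 per arm, 1048 in total. Power at 1048 is 89.99%.
- Attrition: 524 / 0.9 = 582.2, rounded up to 583 per arm, or 1166.

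The stated 524, 90% and 1166 all reproduce with no covariate in the calculation.

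**2. Compare covariate sets.** Proportional-odds trials were simulated with N = 1048, a fixed design, no centre effect and 4000 trials per scenario. Each data set was fitted with the plan's two dichotomies and again with continuous age and NIHSS plus pre-stroke mRS. The protocol gives neither prognostic strengths nor covariate distributions, so both are assumed. The strengths are log odds ratios per SD of age / per SD of NIHSS / per pre-stroke mRS point. Relative effective sample size is (mean z, fuller model ÷ mean z, planned model)².

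| Assumed strength | Mean \|z\|, planned → fuller (conditional OR 0.7) | Relative effective N | Power, marginal OR about 0.7 | Power, conditional OR 0.7 |
|---|---|---|---|---|
| None (0 / 0 / 0) | 3.222 → 3.222 | 1.00 | 89.5% → 89.6% | 89.5% → 89.6% |
| Weak (0.2 / 0.5 / 0.15) | 3.092 → 3.180 | 1.06 | 91.8% → 93.1% | 87.1% → 89.1% |
| Moderate (0.35 / 0.8 / 0.3) | 2.883 → 3.112 | 1.165 | 93.6% → 96.4% | 82.6% → 87.5% |
| Strong (0.5 / 1.1 / 0.4) | 2.684 → 3.049 | 1.29 | 95.6% → 98.5% | 76.2% → 86.4% |

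For example, in the moderate row, (3.112 / 2.883)² = 1.165. Relative effective sample size is practically the same when the marginal OR is held instead: (3.738 / 3.463)² = 1.165.

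**3. Split the gain.** In the order none, weak, moderate, strong:

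- Making age and NIHSS continuous, without pre-stroke mRS, gives about 0%, 4%, 10% and 17%.
- Adding pre-stroke mRS to the dichotomised model gives about 0%, 2%, 7% and 11%.

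**4. Which power column applies.** Section 10.1 does not say whether the OR of 0.7 is marginal or conditional. Step 1 reproduces 524 from the overall control distribution with no covariate, so the marginal column is the closer reading. There the planned model is at or above 90%, within simulation error, in every scenario, and the fuller model adds between 0.1 and 2.9 points.

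**The case against.** The strongest reply is that nothing here is wrong. Adjusting for the minimisation factors in the form used to balance them is coherent and valid, and no figure in the plan is missed. Section 10.5 also does not say that no other covariate may enter. Section 10.3.3 adds baseline EQ-5D-5L for one outcome, and detailed analysis plans for the interim and final analyses are to follow, so pre-stroke mRS could still be added there. All of this stands, and it limits the pre-stroke mRS half of the point to an omission from the named set. It does not remove the explicit two-way cuts, which the protocol itself fixes.

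The size of the gain is also open to challenge. It rests wholly on assumed strengths, and NIHSS is recorded at admission while randomisation may come up to 14 days later, so its gradient could be weaker than supposed. That is why the range starts at zero.

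Three stronger readings are tempting but unsupported:

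- **The trial is underpowered because of its covariates.** The 88.3% in section 10.1 against 89.8% for the full trial is the disclosed price of interim stopping and does not come from the adjustment set.
- **The conditional-OR column shows a shortfall.** Those values fall below 90% because the odds ratio is non-collapsible: fixing the conditional OR at 0.7 implies a weaker marginal effect than the one that reproduces the plan's calculation.
- **The model adjusts for age and NIHSS alone.** Centre is also in it, as a random effect.

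**Conclusion.** The point holds as forgone efficiency in a valid plan. For the primary model, section 10.5 uses age and NIHSS only as dichotomies and does not name pre-stroke mRS, although all three are collected in full. Replacing the dichotomies and adding pre-stroke mRS is worth about 0% (not prognostic), 6% (weak), 16-17% (moderate) or 29% (strong) in effective sample size, or about 0 to 3 power points with the marginal OR near 0.7. In every simulated scenario with prognostic covariates the fuller model gained, and with none it lost nothing.

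The direction is secure wherever the covariates are prognostic, which is likely for pre-stroke mRS. The size is not established by the protocol. It depends on the assumed strengths and covariate distributions, a linear effect of each covariate, proportional odds, a fixed design and no centre effect.

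**What to change.** In section 10.5, for the interim and final primary model, enter age and NIHSS as continuous variables, add pre-stroke mRS, and keep centre as a random effect. Keep the 80-year and NIHSS 12 cuts for minimisation and for the subgroups in section 10.4. Stroke type is optional; it was not part of the calculation.

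Add one sentence on missing baseline covariates, for example a pre-specified single imputation. Section 10.8 makes the main analysis complete case and plans imputation only for missing outcomes, so without such a rule each added covariate could drop participants.

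No new data are needed. The costs are a protocol amendment under section 13.10, matching text in both analysis plans before any unblinded data are seen, and an odds ratio that is conditional on more covariates and should be reported as such.

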10.6 Interim analysis and criteria for the premature termination of the trial

A group sequential approach will be taken. An interim analysis of the primary outcome will be presented to the IDMC after 524 participants (50%) have provided 90-day mRS (primary outcome).

In the event of the following conditions, a recommendation will be made to cease recruitment:

- 1. A treatment effect estimate with z<(-3.09) (one-sided p<0.001 in favour of clarithromycin) on the grounds of efficacy
- 2. A treatment effect estimate with z>(-0.5) on the grounds of futility

If neither condition is met, recruitment will continue to the original target.

The final primary analysis will be judged at a one-sided p value of p<0.025.

10.7 Participant population

Primary efficacy analyses will be undertaken according to the intention to treat principle. Complier average causal effects analysis will be used to estimate the average treatment effect in those treated.

10.8 Potential risk of missing or spurious data

The main analyses will use complete case data. Factors associated with availability of follow-up data will be assessed using logistic regression. Sensitivity analyses will include multiple imputation of missing outcome data.

Data will be gathered from the medical record by investigators. Missing data will be identified and queried by data management on a regular basis.

Participants and consented caregivers will provide their contact details at enrolment for the Day 90 follow-up. Outcome assessors will attempt to contact participants and caregivers to arrange a suitable time to complete the questionnaires. Where possible, data not obtained via telephone follow-up will be gathered from the participants' medical records.

10.9 Other statistical considerations

Interim and final analyses will be carried out according to separate SAPs, written by the trial statistician who will not have access to randomised group allocations. These will be approved prior to unblinded data being seen.

Any deviations to these SAPs (e.g. changes to planned analysis method due to non-compliance with modelling assumptions) will be documented as part of the statistical outputs produced.

10.10 Economic evaluation

Economic evaluation will be performed by the Manchester Centre for Health Economics, University of Manchester. It will compare the cost and outcomes of standard care with standard care plus clarithromycin in PSP from the NHS/Personal Social Services perspective, using established quality criteria [38,39]. The impact of caregiver health and cost burden will also be explored [40].

Within-trial Cost-effectiveness Analysis – Will compare the difference in total health and social care cost and health outcomes for standard care with standard care plus clarithromycin over the study follow-up period (90 days).

Healthcare resource use per participant will be measured at baseline and at day 90 using routine data collection and a purposely designed healthcare services utilisation form (developed with the PPIE Group). Individual-level costs will be created by combining measured resource use with published unit costs. Costs will comprise:

- Secondary care (days spent on stroke unit, rehabilitation wards, general medical wards, intensive care unit, readmissions, Accident & Emergency, outpatient visits)
- Primary care (GP practice visits and phone contacts with the GP practice personnel)
- Time in care homes.

We will collect downstream health and social care costs and informal caregiver costs using an adapted Client Service Resource Inventory (CSRI) [41], combined with an adapted version of the Costs of Family Caregiving in Palliative Care(COFAC tool [42]). The COFAC tool has been shown to be valid, acceptable to caregivers and feasible to administer. The COFAC questionnaire seeks to capture data from a broad societal perspective which includes family caregiver costs. Health outcomes will be expressed as quality-adjusted life-years (QALYs). The EQ 5D-5L questionnaire will be administered to patients (or a proxy score from their caregivers) at baseline and at Day 90, so that QALYs can be calculated for each participant, using the area under the curve method. Following the NICE Reference Case, EQ-5D-5L responses will be converted to EQ-5D-3L utility values [43]. We will collect EQ-5D for caregivers and generate QALYs in the same way.

Generalised linear model regression will estimate the total cost and total QALYs per arm controlling for baseline cost, baseline health utility, and other relevant participant characteristics. Bootstrapping will be used to handle stochastic uncertainty. The incremental cost-effectiveness ratio (ICER) will be calculated if either strategy is not dominated. Missing data will be handled using multiple imputation. Sensitivity analyses will investigate the robustness of the estimated ICER to different analysis assumptions.

Model-based Cost-effectiveness Analysis – Will compare the difference in cost and health outcomes for standard care with standard care plus clarithromycin over a lifetime time horizon (discount rate: 3.5%). A de novo cohort-level Markov model with an embedded decision tree will be developed to simulate the natural history of PSP and the impact of the intervention, with input from patients and clinicians.

Systematic reviews of existing cost effectiveness models in PSP, HAP, CAP and stroke will inform model structure. The Markov model health states will take into account level of disability from stroke using mRS scores [44]. Patient characteristics, transition probabilities, resource use and utilities associated with the two regimens will be taken from the trial population. Transition probabilities, resource use and utilities associated with stroke disease progression will be obtained from published evidence.

A probabilistic base case analysis will account for all input parameter uncertainty simultaneously. We will report total and incremental cost and QALYs, and ICER (if relevant). A cost-effectiveness threshold of £20-30,000 per QALY gained will be used to determine cost-effectiveness. A cost-effectiveness acceptability curve will report the probability of cost effectiveness and incremental net monetary benefit will be derived. Deterministic one-way sensitivity analyses will identify key drivers of cost-effectiveness. Potential scenario analyses include:

- 1. Alternative mapping methods to estimate EQ-5D-3L utility values from mRS
- 2. Inclusion of carer utility
- 3. Inclusion of carer costs.

Subgroup analysis will include stroke type, interval since admission, and whether the patient had received thrombolysis or thrombectomy.

11 DATA MANAGEMENT

11.1 Source data

ICH GCP defines source data as 'All information in original records and certified copies of original records of clinical findings, observations or other activities in a clinical trial necessary for the reconstruction and evaluation of the trial.' In this study, the location of the source data will be detailed in Source Data Plans completed by each site. The source data transcribed into the eCRF from the medical records must be accurate and verifiable.

Outcome data for mRS, SIS, EQ-5D-5L and Zarit Caregiver Burden (ZBI-12) will be entered directly into the eCRF by assessors at the central unit carrying out follow-up. The eCRF entry will act as source data for follow-up information.

Where postal questionnaires are required to gather outcome data, paper copies of these questionnaires will be the source data.

11.2 Data collection

An eCRF, developed by the Robertson Centre for Biostatistics, will capture all data required to meet this protocol's requirements. Data will be stored in a MS SQL Server database. Access to the eCRF will be restricted via a study-specific web portal.

Authorised site staff will be able to make entries to their patients' data via the web portal. The Investigator (or their designee) will be responsible for all entries into the eCRF and will confirm that the data are accurate, complete and verifiable excluding the Day 90 visit.

Trained staff assessing Day 90 visit clinical outcomes (centralised and blinded assessments) will be authorised access to the web portal to make entries to the Day 90 visit pages.

Direct access to the web portal will be granted on request to authorised representatives from the Sponsor, host institution and the regulatory authorities to permit trial-related monitoring, audits and inspections.

11.3 Data validation

Where it is practical, data will be validated at the point of entry into the eCRF. Any additional data discrepancies will be flagged to the investigator and any data changes will be recorded to maintain a complete audit trail (reason for change, date change made, who made change).

11.4 Data security

Robertson Centre for Biostatistics systems are fully validated in accordance with industry and regulatory standards, and incorporate controlled access security. High volume servers are firewall protected and preventative system maintenance policies are in place to ensure no loss of service or data. Web servers are secured by digital certificates. Data integrity is assured by strictly controlled procedures, including secure data transfer procedures. Data are backed up on-site nightly and off-site to a commercial data vault weekly. The RCB has an ISO 9001 quality management system and ISO 27001 for Information Security, and is regularly inspected against the standards by the British Standards Institution.

